3.1 Background

Irritable bowel syndrome (IBS) is a gastrointestinal (GI) syndrome characterized by chronic abdominal pain and altered bowel habits in the absence of any organic cause. The symptoms of IBS not only adversely affect a patient's health-related quality of life (QoL), but also place a significant financial burden on society due to reduced work productivity and increased use of healthcare-related resources^{1,2}. Patients with IBS frequently complain of abdominal bloating and increased gas production in the form of flatulence or belching. The prevalence in North America and Europe is approximately $10-15\%^{3,4}$. Irritable bowel syndrome affects all ages and genders however there is a 2:1 female predominance in North America⁵. Irritable bowel syndrome is classified into 4 subtypes based on stool pattern: IBS with constipation (IBS-C), IBS with diarrhea, mixed IBS, and un-subtyped IBS. Irritable bowel syndrome with constipation is defined as the presence of hard or lumpy stools with \geq 25 percent of bowel movements and loose or watery stools with < 25% of bowel movements⁶.

SYN-010 is a modified release, oral formulation of lovastatin being developed for the treatment of IBS-C. The SYN-010 program is based predominantly on research by [name] (Director, Medically Associated Science and Technology Program, Cedars-Sinai Medical Center) and collaborators^{7,8,9} hypothesizing that reduction in intestinal methane (methane) production can reverse constipation and improve global symptoms in IBS-C. Methane production in humans is due to methanogenic archaea in the intestine, predominantly *Methanobrevibacter smithii* (*M. smithii*). Methane, the key product of anaerobic respiration of methanogens, had been perceived to produce no ill effects in humans aside from gaseous distention. However, several research groups worldwide have shown that a significant percentage of patients with IBS-C excrete methane, and elevated methane production by methanogens correlates with constipation and related symptoms in both IBS-C and chronic idiopathic constipation^{7,8,9,10,11,12,13}. A direct causative role for methane in IBS-C was demonstrated in a recent case report, wherein a woman undergoing fecal microbiota transplantation (FMT) for *C. difficile* infection unknowingly received stool containing a high concentration of methanogens. The FMT recipient rapidly developed severe symptoms of IBS-C that were subsequently reversed by ablation of methane production¹⁴.

Further details can be found in the Investigator's Brochure, which contains comprehensive information on the investigational product.

3.2 Summary of findings from pre-clinical studies with potential clinical significance

A series of preclinical studies have sought to understand the mechanism by which methane exerts its effects on gastrointestinal motility. The precise mechanism remains under investigation; however, these studies indicate that methane may exert its actions in the intestine by modulation of the cholinergic pathway of the enteric nervous system¹⁵. *In vivo* studies in dogs and *ex vivo* studies using guinea pig ileal strips showed that methane stimulates non-propagating contractions, preventing propulsion of materials through the intestinal tract^{16,17}.

The active ingredient of SYN-010 is lovastatin lactone, which was first approved by the FDA in 1987; it is a cholesterol-lowering agent (Mevacor[®], Merck & Co., Inc.)¹⁸ and has a history of safe use at oral doses up to 80 mg/day. In its cholesterol-lowering indication, lovastatin lactone is a prodrug and must be converted to the β -hydroxyacid form to inhibit the enzyme HMG-CoA reductase (HMGR). The preclinical safety of lovastatin lactone and β -hydroxyacid was established in detailed preclinical and toxicology studies conducted by Merck¹⁹.

Interest in lovastatin as a potential inhibitor of methanogenesis originated with recognition that the rate-limiting step in the synthesis of lipid membranes in the methanogen *M. smithii* is catalyzed by HMGR. As detailed below, it has since been determined that HMGR is not the target for lovastatin anti-methanogenic activity and the methane reducing effects of SYN-010 can be separated from potential systemic effects such as cholesterol lowering.

The ability of lovastatin to inhibit methane production was established in *ex vivo* studies investigating the effects of nine statins (including lactone and β -hydroxyacid forms) on methane production by stool samples from IBS-C patients. In these studies, lovastatin lactone was identified as the only effective statin inhibitor of methane production, while the cholesterol-lowering metabolite lovastatin β -hydroxyacid was ineffective. In fact, the β -hydroxyacid forms of pravastatin, simvastatin, rosuvastatin and atorvastatin were all ineffective inhibitors of methane production in his system. These experiments also demonstrated the dose-dependence of methane inhibition by lovastatin lactone and a head-to-head comparison of lovastatin lactone, lovastatin lactone-diol and lovastatin β -hydroxyacid affirmed that the lactone form of lovastatin is the anti-methanogenic species²⁰.

An additional important feature of lovastatin as a methane lowering agent is that neither lovastatin lactone nor the β -hydroxyacid appear to be microbicidal. Neither species eradicated *M. smithii* or bacteria in the intestine of rats administered daily oral doses of each compound for 10 days²¹.

3.3 Rationale of the study

SYN-010 has previously been evaluated in consecutive Phase 2a clinical trials. Sixty-three (63) IBS-C patients with high breath methane (>10 ppm) at screening were enrolled in a multicenter, randomized, controlled, double-blinded clinical trial (RCT) in which they received SYN-010 21 mg, SYN-010 42 mg or Placebo once daily for 4 weeks. Fifty-four (54) subjects who completed the RCT continued into an open-label extension (EXT) in which all subjects received SYN-010 42 mg once daily for an additional 8 weeks.

The SYN-010 Phase 2a studies were intentionally designed as mechanistic proof-of-concept studies, wherein reductions in breath methane were employed as a rapid and cost-effective means by which to determine if SYN-010 could be effective in treating an underlying cause of symptoms in IBS-C. Breath methane was reduced relative to baseline in SYN-010 treatment groups, and lower breath methane levels correlated with an increased number of complete spontaneous bowel movements (CSBMs) at week 12, consistent with the proposed methane-inhibiting action of lovastatin lactone²².

Since lovastatin has not previously been used to treat IBS-C patients, the SYN-010 Phase 2a studies were also focused on the safety of the SYN-010 dosage form. Daily doses of SYN-010 were well-tolerated by IBS-C patients over the 12-week treatment period (at least 8 weeks of SYN-010 42 mg). SYN-010 did not cause clinically meaningful or persistent changes in serum liver and muscle markers in IBS-C patients at daily doses of 21 mg and 42 mg. Modest decreases from baseline in lipid parameters observed after 7 days of SYN-010 21 mg or 42 mg had largely faded by 28 days and were not evident after 12 weeks of dosing²³. Very few adverse events were reported over 12 weeks of SYN-010 treatment and all were of mild or moderate intensity. No serious adverse events were reported and there were no incidences of drug-related diarrhea, which is an important potential benefit of SYN-010 as an IBS-C therapy.

Although the Phase 2a studies were not prospectively powered for formal statistical evaluation of clinical endpoints, compelling improvements in CSBMs, abdominal pain, and bloating were observed in SYN-010 treatment groups. These clinical findings have been presented in multiple public forums

and a panel of clinical advisors affirmed that the Phase 2a data validate the need to evaluate optimal dosing of SYN-010 in a larger patient population over a longer dosing period.

Based on the potential clinical benefit observed in Phase 2a, this Phase 2b clinical study will evaluate in more detail the clinical effects of two dose strengths of SYN-010 administered over a longer treatment period (12 weeks per FDA guidelines) to a larger number of IBS-C patients. The study will seek more definitive evidence regarding potential symptom improvements and safety in IBS-C patients. The study also seeks to provide new information of relevance to both efficacy and safety by measuring changes to the microbiome in patient stool samples; serum level of cytokine markers of inflammation; and expanded breath gas measurements.

3.4 SYN-010 (lovastatin lactone modified release capsules)

3.4.1 Description

SYN-010 is a hydroxypropyl methylcellulose (HPMC) capsule filled with enteric-coated tablets from which lovastatin is released at different intestinal pH values. The tablets are designed to pass through the stomach unchanged then release a small amount of lovastatin into the duodenum and the majority of the lovastatin dose into the ileocecal junction and colon. The amount of lovastatin to be released into the small and large intestine is anticipated to be consistent with the relative levels of methane-producing archaea in each location of the intestine²⁴.

Each tablet in the SYN-010 dosage form contains 7 mg of lovastatin combined with USP excipients and coated with two different EUDRAGIT[®] enteric polymers that dissolve at either pH 5.5 (duodenal release; DR) or pH 7.0 (ileocecal release; ICR).

- SYN-010, 21 mg (D1-I2) comprises an opaque, green, size 1 HPMC capsule containing 1 x pH 5.5-coated tablet (DR) and 2 x pH 7.0-coated tablets (ICR).
- SYN-010, 42 mg (D1-I5) comprises an opaque, green, size 1 HPMC capsule containing 1 x pH 5.5-coated tablet (DR) and 5 x pH 7.0-coated tablets (ICR).

3.4.2 Mechanism of action

Methane production (methanogenesis) is a ubiquitous process in the human intestine, disposing of hydrogen and other by-products formed during bacterial fermentation. Methane production in humans is almost entirely due to the archeon *M. smithii*. Elevated intestinal methane production reduces intestinal motility and is a cause of constipation, pain and bloating in IBS-C.

Interest in lovastatin as a potential inhibitor of methanogenesis originated with recognition that the rate-limiting step in the synthesis of archaeal lipid membranes is catalyzed by HMG-CoA reductase (HMGR) which is the target enzyme for cholesterol-lowering statins. Subsequent *in vitro* studies (described above) and computational studies have since determined that HMGR is not the target for lovastatin anti-methanogenic activity; rather, lovastatin lactone appears to exert a direct effect on methanogenesis enzymes. The mechanism by which lovastatin lactone inhibits methane production by *M. smithii* has not been conclusively determined; however, detailed computational studies showed that lovastatin lactone may competitively inhibit F420-dependent methylenetetrahydromethanopterin dehydrogenase (mtd), an enzyme that is integral to the *M. smithii* methanogenesis pathway²⁵.

Date: June 30, 2020

Methanogenic archaea reside predominantly in the human colon, with lower methanogen levels measured in the small intestine of some patients. Methane production at both sites contributes to reduced gastrointestinal motility and rat studies suggest that the ileocecal region may be of particular significance²¹. SYN-010 utilizes a dual-pulse release profile to deliver a portion of the lovastatin dose to the small intestine and the majority of the dose to the ileocecal junction and colon where the most methane-producing organisms are found; the relative amounts of lovastatin released into the small and large intestine are consistent with the anticipated relative levels of methanogens in each location.

Lovastatin lactone exerts its methane-reducing effect in the intestinal lumen and systemic absorption of lovastatin is not required for its therapeutic effect in IBS-C. The pharmacokinetic profile of SYN-010 has been evaluated in a repeated-dose study in heathy volunteers. Two of the most therapeutically relevant findings from the PK study were:

- Conversion of the anti-methanogenic lovastatin lactone to the cholesterol-lowering βhydroxyacid metabolite was significantly reduced in the SYN-010 formulation, and this was reflected in reduced systemic levels of the β-hydroxyacid and an absence of clinically meaningful or persistent SYN-010 effects on serum liver, lipid and muscle markers;
- Conversion of the anti-methanogenic lovastatin lactone to the cholesterol-lowering βhydroxyacid metabolite was significantly reduced in the SYN-010 formulation, and this was reflected in reduced systemic levels of the β-hydroxyacid and an absence of clinically meaningful or persistent SYN-010 effects on serum liver, lipid and muscle markers.

In addition to the pharmacokinetic study, sparse PK sampling was conducted in IBS-C patients during Phase 2a clinical testing. After daily administration of SYN-010 21 mg or SYN-010 42 mg, plasma trough levels of both lovastatin lactone and β -hydroxyacid were low and variable, such that \geq 50% of patients had undetectable plasma levels of each lovastatin species after both 7 and 28 days of treatment²³. Reduced systemic levels of lovastatin species and high concentrations of lovastatin lactone in the stool are compelling findings regarding the use of SYN-010 as an intestine-acting anti-methanogenic therapy.

4. Study objectives

4.1 Primary

Change from baseline in the weekly average number of CSBMs during the 12-week Treatment Period for SYN-010 relative to placebo.

4.2 Secondary

Safety and tolerability of SYN-010 21 mg and 42 mg in IBS-C patients treated for 12 weeks.

For SYN-010 relative to placebo:

- Proportion of overall stool frequency responders.
- Proportion of overall bloating responders.
- Proportion of patients using rescue medication.

- Proportion of overall responders in the SYN-010 21 mg and 42 mg treatment groups versus placebo.
- Change from baseline for SYN-010, relative to placebo, in:
 - Weekly average score for worst abdominal pain at Weeks 1 through 12.
 - Weekly average number of CSBMs at Weeks 1 through 12.
 - Weekly average number of SBMs at Weeks 1 through 12.
 - Weekly average bloating score at Weeks 1 through 12.
 - Weekly average stool consistency (BSFS) at Weeks 1 through 12.

4.3 Exploratory

Date: June 30, 2020

For SYN-010 relative to placebo:

- Proportion of patients with adequate relief²⁷.
- Change from baseline for SYN-010 in patient reported outcomes (PRO) using validated questionnaires in the REDCap system.
- Breath gas area-under-the-curve (AUC) (methane, hydrogen, and hydrogen sulfide) on lactulose breath test at EOS compared to Screening.
- Spot breath tests at Randomization, Day 28, and Day 56.
- Comparison of serum cytokine levels at baseline and EOS measuring for potential immune or inflammatory signals to include the key cytokines of the Th1/Th2/Th17 pathways: IL-2, IL-4, IL-5, IL-9, IL-10, IL-13, IL-17, GM-CSF and IFN-γ. Plus TNF-α, IL-12, IL-6, the two chemokines IL-8 and MCP-1, and the gut cytokine IL-25.
- Microbiome measurements in stool of bacteria (16S rRNA) and methanogens (qPCR).

5. Study design and investigational plan

5.1 Pre-treatment period

Screening and Pre-treatment Period (up to 17 days prior to the first dose of study drug):

During the Screening and Pre-treatment Period, patients will be provided an ID number and password-protected access to the REDCap website to record baseline parameters (such as weekly average worst abdominal pain score and weekly number of CSBMs). During this period, patients will also (i) complete a lactulose breath test including analysis of methane, hydrogen, hydrogen sulfide, and carbon dioxide; (ii) provide a stool sample for analysis of the microbiome; and (iii) provide a blood sample for analysis of cytokines and baseline tests. Patients will be eligible for randomization if they have a breath methane level of \geq 10 ppm on the lactulose breath test and fully respond to the PRO questionnaires in the REDCap system on at least 11 of 14 days of the Screening and Pretreatment Period.

5.2 Treatment phase

Treatment Period comprising Randomization (Day 1) and 12 weeks of dosing (with clinic visits at Weeks 4, 8, and 12).

On Day 1, eligible patients will be randomized in a 1:1:1 ratio to receive study drug (SYN-010 21 mg, SYN-010 42 mg, or placebo). Study drug will be administered during the Treatment Period and taken once daily at bedtime for up to 12 weeks.

5.3 Post-treatment period or follow-up period

End-of-Study contact between 24 and 48 hours after Week 12 for patients who complete the Treatment Period.

6. Statistical methods and determination of sample size

6.1 General considerations

A statistical analysis plan (SAP) describing all the statistical analyses to be completed will be finalized prior to database lock. Unless otherwise specified, for numeric data, descriptive statistics will include the number of patients with data to be summarized (n), mean, standard deviation (SD), median, minimum (min), and maximum (max). Categorical data will be presented using frequency counts and percentages. All statistical tests will be conducted at a 2-sided significance level of 5% unless otherwise specified.

6.2 Disposition of patients

Patient disposition will be summarized for the study, along with reasons for early termination. Numbers (%) of patients in each analysis population will be tabulated.

6.3 Protocol deviations

All protocol deviations will be reviewed and documented before database lock. Protocol deviations will be recorded by the site staff, and study monitor. Major protocol deviations will be defined in the SAP before unblinding the study.

6.4 Analysis populations

Three analysis populations are defined for this study:

- The randomized patient population will consist of all patients who are randomized;
- The full analysis set will consist of all randomized patient who receive at least one dose of study drug. The full analysis set will be used for the efficacy and safety analyses. Efficacy analysis will be conducted according to the randomized treatment the patients receive, and safety analysis will be conducted according to the actual treatment the patients receive;
- The per-protocol set will consist of all patients in the full analysis set who do not have major protocol deviations as defined in the SAP.

6.5 Demographics and baseline characteristics

Demographics and baseline characteristics will be summarized by treatment for the full analysis set. Demographics and baseline characteristics of the patient sample will be described using summary statistics.

6.6 Efficacy analyses

The primary endpoint is the change from baseline in the weekly average number of CSBMs during the 12-week Treatment Period.

The secondary endpoints are defined as below:

- Proportion of overall responders during the 12-week Treatment Period (overall 12-week responders). An overall 12-week responder is defined as a patient with a weekly response in at least 50% of the weeks of treatment (6 of 12 weeks). A weekly response is defined as a decrease in the patient's weekly average score for worst abdominal pain in the past 24 hours of at least 30% compared to baseline and a stool frequency increase of 1 or more CSBMs per week compared with baseline.
- Proportion of overall stool frequency responders during the 12-week Treatment Period. An overall stool frequency responder is defined as a patient with a weekly stool frequency response in at least 50% of the weeks of treatment (6 of 12 weeks). A weekly stool frequency response is defined as a stool frequency increase of 1 or more CSBMs per week compared with baseline, with abdominal pain unchanged or improved compared with baseline.
- Proportion of overall abdominal pain intensity responders during the 12-week Treatment Period. An overall abdominal pain intensity responder is defined as a patient with a weekly abdominal pain intensity response in at least 50% of the weeks of treatment (6 of 12 weeks). A weekly response abdominal pain intensity response is defined as a decrease in the patient's weekly average score for worst abdominal pain in the past 24 hours of at least 30% compared to baseline, with stool frequency unchanged or improved compared with baseline.
- Proportion of overall bloating responders during the 12-week Treatment Period. An overall bloating responder is defined as a patient with a weekly bloating response in at least 50% of the weeks of treatment (6 of 12 weeks). A weekly bloating response is defined as a weekly average bloating score of at least 30% improvement compared to baseline, with stool frequency unchanged or improved compared with baseline.
- Proportion of patients using rescue medication.

Additional secondary endpoints are change from baseline. The change from baseline at Visit X is defined as Value at Visit X – Value at Baseline. The percent change from baseline is defined as (change from baseline)/baseline value. If the baseline value = 0 or missing, then the percent change from baseline will be missing.

- Change from baseline in weekly average score for worst abdominal pain at Weeks 1 through 12.
- Percent change from baseline in weekly average score for worst abdominal pain at Weeks 1 through 12.
- Change from baseline in weekly average number of CSBMs at Weeks 1 through 12.
- Change from baseline in weekly average number of SBMs at Weeks 1 through 12.
- Change from baseline in the weekly average bloating score at Weeks 1 through 12.
- Change from baseline in weekly stool consistency score (BSFS) at Weeks 1 through 12.
- Proportions of overall abdominal pain intensity responders with different cutoff points for the % improvement from baseline in weekly average score for worst abdominal pain, i.e., ≥ 10%, 20%, 40%, 50%, 60% and 70%.
- Proportions of overall stool frequency responders with different cutoff points for the improvements from baseline in the weekly number of CSBMs ≥ 2, 3, 4, 5, and 6.
- Proportions of patients with improvements of ≥ 10%, 20%, 30%, 40%, 50%, 60%, and 70% from baseline in the weekly average bloating score in at least 50% of the weeks of treatment (6 of 12 weeks).

The exploratory endpoints are defined as below:

- Proportion of patients with adequate relief²⁶.
- Change from baseline for SYN-010 in patient reported outcomes (PRO) using validated questionnaires in the REDCap system.
- Change from baseline in the area-under-the-curve (AUC) of breath CH₄ production, based on the 120-minute lactulose breath test.
- Change from baseline in breath CH₄ production based on a single-point breath CH₄ test.

The efficacy analyses will be conducted based on the full analysis set and per-protocol set. The analysis for the primary endpoint will be performed using the analysis of covariance (ANCOVA) with treatment group and the baseline value as covariates. The primary analysis will be conducted using the observed values. For missing data, two sensitivity analyses will be conducted by using the multiple imputation and last observation carried forward (LOCF) methods. Details will be included in the SAP.

For missing data imputation, the primary analysis will be conducted based on the following imputation method: If a subject drops out of the study or otherwise does not report efficacy data for a particular treatment period week, the subject will not be considered a responder for that week. The weekly response will not be considered a responder if there are more than three days with missing assessments during a week.

Due to the COVID-19 pandemic, study enrollment was temporarily stopped, at which time a total of 53 patients had been randomized to study drug treatment groups. 49 of these patients have completed the study and 4 have withdrawn or early terminated. A futility interim analysis will be conducted based on the data from these 53 patients. A recommendation to stop enrollment of the study will be made by the unblinded statistician(s) if, for both dose groups, the conditional power is less than 20% based on the primary endpoint AND the difference of the overall 12-week responder rates is less than 2%. The interim analysis will be conducted by a group of people that are not involved in the daily activities of the study. Details will be included in the SAP.

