6.8 Determination of sample size

The sample size calculation is based on the following assumptions: the weekly CSBM change from baseline is 0.5 for the placebo group, and 1.5 for each active group, with common standard deviation of 1.5; 50 patients in each group will have 90% power for each SYN-010 group compared with the placebo by using the t-test with alpha=0.05.

7. Study population

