## 2. PURPOSE

[figure not shown]
This Statistical Analysis Plan (SAP) is based on Protocol Version 3.0 (9 January, 2019) and it describes in detail the statistical methodology and the statistical analyses to be conducted for the above-mentioned protocol.

Results obtained from the analyses outlined in this document will become the basis of the final clinical study report for this protocol. The purpose of this plan is to provide specific instructions as to how each analysis will be conducted.

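### Is the futility rule defective because the protocol does not name the effect assumed in its conditional power?

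*Protocol*

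**What the plan says.** Protocol 6.6 introduces a futility analysis of the 53 patients randomized before the COVID-19 pause, of whom 49 completed and 4 withdrew or stopped early. Unblinded statisticians recommend stopping enrolment when two conditions hold in each of the SYN-010 arms: "the conditional power is less than 20% based on the primary endpoint AND the difference of the overall 12-week responder rates is less than 2" per cent. People outside the daily running of the study carry out the analysis. On method, the section adds only: "Details will be included in the SAP". The synopsis adds nothing on how conditional power is computed.

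The general deadline for the SAP is in Protocol 6.1: "A statistical analysis plan (SAP) describing all the statistical analyses to be completed will be finalized prior to database lock". Protocol 6.3 is stricter on one item: "Major protocol deviations will be defined in the SAP before unblinding the study". No similar sentence covers the interim method.

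The supplied protocol is Version 8.0, dated June 30, 2020. SAP section 2 says of its own basis: "This Statistical Analysis Plan (SAP) is based on Protocol Version 3.0 (9 January, 2019". Neither its contents list nor its text has a section on an interim look, futility or conditional power.

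**The concern.** Conditional power is the chance of a significant final result given the interim data and an assumed effect for the remaining patients. Without that effect, the 20% limit does not define a cut-off. Three choices are usual: the effect used for the sample size, the effect seen so far, or no effect from here on. They can give very different answers from the same data.

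The deferral to the SAP leads to no text in the documents supplied, and the only general SAP deadline is database lock. On paper, the statisticians who make the recommendation could therefore choose the assumption after seeing unblinded results. At stake is whether enrolment resumes after the pause, up to 150 - 53 = 97 further patients. SAP section 2 also says of itself: "The purpose of this plan is to provide specific instructions as to how each analysis will be conducted". That makes the missing section look like an omission.

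**Working it through.** **Inputs.** Protocol 6.8 assumes that "the weekly CSBM change from baseline is 0.5 for the placebo group, and 1.5 for each active group, with common standard deviation of 1.5", so the design effect is 1.5 - 0.5 = 1.0 with SD 1.5. It plans 50 patients per arm, and SAP 2.2 gives two-sided alpha 0.05. The interim has 53 patients (Protocol 6.6). Assumed here: an equal split (53/3 = 17.67 per arm), SD 1.5 at the look, and information proportional to patients, so t = 53/150 = 0.353.

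**The plan's own figure.** The expected final Z is 1.0 / (1.5 × √(2/50)) = 1.0/0.30 = 3.33. Power is Φ(3.33 - 1.96) = 91.5%, or 91.0% with the t distribution. The stated 90% is reproduced.

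**Conditional power.** CP = Φ[(Z₁√t + θ(1 - t) - c) / √(1 - t)], with c = 1.96. Here θ = 3.33 (design effect), Z₁/√t (observed trend) or 0 (no further effect). Setting CP = 0.20 gives

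Z₁√t + θ(1 - t) = 1.96 - 0.842 × √0.647 = 1.283.

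The interim standard error is 1.5 × √(2/17.67) = 0.505.

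| Reading | Z₁ limit | Interim difference (CSBMs/week) | CP at 0 | CP at +0.5 | CP at +1.0 |
|---|---|---|---|---|---|
| Design effect | -1.468 | -0.74 | 59.6% | 83.5% | 95.6% |
| Observed trend | 0.763 | +0.385 | 0.7% | 35.8% | 95.6% |
| No further effect | 2.159 | +1.09 | 0.7% | 4.4% | 16.5% |

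The limits span 1.83 against a planned effect of 1.0. Other open details matter less:

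- Counting only the 49 completers (t = 0.327) gives -0.90, +0.38 and +1.17.
- A final critical value of 2.24, for the 0.025 step of the Hochberg procedure in SAP 8.1, gives -0.50, +0.47 and +1.33.

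**Conditional-power condition alone, both doses** (bivariate normal, correlation 0.5 from the shared placebo arm). This is an upper bound on stop recommendations.

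| Truth | Design effect | Observed trend | No further effect |
|---|---|---|---|
| Neither dose works | 2.0% | 66% | 97% |
| Both work as planned | under 0.1% | 3.8% | 41% |
| One works | 0.02% | 10.8% | 56.9% |

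**The rule as written.** A stop also needs the responder difference to be below 2% in both doses. The documents give no responder rates, so they are assumed: 10-40% with no effect, 20 points higher when both doses work, and latent correlation 0.3-0.8 with the primary endpoint. Each setting used 60,000 simulated trials.

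| Truth | Design effect | Observed trend | No further effect |
|---|---|---|---|
| Neither dose works | 1.1-1.9% | 26-37% | 34-46% |
| Both work | under 0.1% | 0.2-1.2% | 1.2-3.9% |

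If neither dose works, the responder condition alone holds in both doses in 34-46% of trials. In the other 54-66%, every reading gives the same answer: no stop.

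**Dates.** The supplied SAP rests on a protocol of January 2019. The look was prompted by a pandemic pause and appears in a protocol dated June 2020. A plan built on the earlier version could not describe it. The SAP also says its results form the basis of the final study report, so its sentence about specific instructions concerns the final analyses.

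**The case for a change.** The strongest case for a change is that a later SAP, even if it exists, need not have been written before the look. The protocol could have required this, as it did for major deviations, and did not. The reading is also consequential under the whole rule: with two ineffective doses, the design-effect reading almost never recommends a stop, while the other two do so in roughly a quarter to nearly half of trials. One sentence would settle it.

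Much of this stands. The assumption is unstated, no supplied text dates it before the look, and 1-2% against 26-46% is a real difference. Two things do not follow.

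- Nothing says the choice will be made after unblinding. The protocol already fixes the 20% and 2% limits, their joint use, the both-doses requirement and the data set, and it keeps the analysis away from those running the trial.
- The most striking figures, 97% and 41%, describe one condition and not the rule. For two effective doses, the responder condition brings the 41% down to at most 3.9%.

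One limit of the check remains. With a single effective dose, only the upper bound was computed, and it is wide under the no-further-effect reading.

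**Conclusion.** The observation is correct, but it calls for no change to the plan. Protocol 6.6 leaves a technical detail to a document still to be written, and the analysts can fill it with any of three legitimate choices. No stated rule contradicts another and no number is wrong. There is no ground for preferring one reading over the sponsor's own choice, so the remedy would only be to write that choice down and date it, which the promised interim details would ordinarily do.

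The consequences are bounded. The rule cannot stop for efficacy, so type I error is not inflated. Wrongly recommending a stop when both doses work occurs in at most about 4% of trials under any reading. The reading least likely to stop simply lets the trial run to its planned 150 patients. What varies is the chance of stopping two ineffective doses: about 1-2%, 26-37% or 34-46%.

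These full-rule figures rest on assumed responder rates of 10-40%, a 20-point rise when both doses work, correlations of 0.3-0.8, SD 1.5 and a near-equal split of the 53 patients. The case of one effective dose under the full rule was not quantified.
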